2.1.2. Primary assessment criterion

The primary endpoint is the occurrence of pressure ulcers of grade ≥ 1 on the NPUAP scale at the catheter/extender junction. The assessment will be carried out blind by a childcare assistant from the department.

2.2. *SECONDARY OBJECTIVES AND EVALUATION CRITERIA*

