2.2.1. Secondary objective(s)

- Compare the severity of pressure ulcers at the catheter/tube junction.
- Compare the duration of peripheral venous catheter retention between the two groups.
- Compare the rate of nosocomial infections related to peripheral venous catheters between the two groups.

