4.5. DESCRIPTION OF THE EVALUATION AND DATA COLLECTED

The primary endpoint is the development of a pressure ulcer of grade ≥ 1 on the NPUAP scale at the catheter/tubing junction.

This area is assessed several times a day by nurses, who remove the bandage without removing the fixation device (compress and transparent adhesive dressing). However, if the compress is soiled, the dressing will be changed.

NPUAP scale

The NPUAP pressure ulcer assessment scale, translated from English by ANAES, will be used. This scale allows pressure ulcers to be assessed according to four stages, graded from 1 to 4, with stage 1 being the least severe.

- Stage I: The first stage is an observable change in intact skin, related to pressure and manifested by a change in one or more of the following characteristics compared to the adjacent or contralateral body area: skin temperature (warm or cold), tissue consistency (firm or soft) and/or sensitivity (pain, itching). In people with fair skin, the pressure ulcer appears as persistent localised redness, while in people with pigmented skin, the pressure ulcer may be a persistent red, blue or purplish colour.

Example: Stage 1 pressure ulcer

- Stage II: Loss of part of the skin's thickness; this loss affects the epidermis, the dermis, or both. The pressure ulcer is superficial and clinically presents as an abrasion, blister, or shallow ulceration.

- Stage III: Loss of all skin thickness with alteration or necrosis of the subcutaneous tissue; this may extend to the fascia, but not beyond. The pressure ulcer appears clinically as a deep ulceration with or without invasion of surrounding tissues.
- Stage IV: Loss of the entire thickness of the skin with significant tissue destruction, or involvement of muscles, bones, or supporting structures (e.g., tendons, joints). Invasion and fistulas may be associated with stage IV pressure ulcers.

The catheter will be removed by the nurse in charge of the patient.

In order to allow for a blind assessment of the primary endpoint, this will be performed by a childcare assistant from the department who is on duty 24 hours a day and has not previously cared for the child. The childcare assistant will assess the pressure area and then note their observations in the patient's file (presence or absence of pressure ulcers and NPUAP grade, if applicable).

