4.6. IDENTIFICATION OF ALL SOURCE DATA NOT INCLUDED IN THE MEDICAL RECORD

Source data not included in the medical record corresponds to data not routinely collected in the medical and paramedical records.

In this study: The assessment by the childcare assistant of the grade of pressure ulcer reported on a data collection sheet will be considered as the source data.

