5.2. STATISTICS

Responsible for statistical analysis:

[name]
Vendée Departmental Hospital Centre
Clinical Research Unit
[contact]

Software

The analyses will be performed using R software version 3.5.1

5.2.1. Description of planned statistical methods, including the schedule for planned interim analyses

All variables will be described globally and by group. The description will include the numbers and percentages of modalities for qualitative variables and the minimum, maximum, mean, standard deviation and median for quantitative variables.

Primary endpoint

The primary endpoint is defined as the presence of a pressure ulcer at the junction of the catheter with the extension tube or peripheral venous line tubing. The assessment will be performed upon catheter removal and blinded by a nursing assistant from the department.

The percentage of patients will be presented with a 95% confidence interval in the two groups and will be compared using a Chi-square test.

In a second step, the two groups will be compared using logistic regression to take into account the duration of catheter retention.

Secondary criteria

The severity of pressure ulcers will be described between the two groups. At each stage of the NPUAP scale, the number and percentage of patients will be presented. A Mann-Whitney test will be applied to compare the two groups.

The average duration of catheter retention will be described for the two groups with a 95% confidence interval. It will be compared using a Student's t-test.

The number of patients with nosocomial infection will be described in the two groups. No statistical test will be performed.

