Appendix 1) Catheter insertion protocol with compress

Appendix 2) Catheter placement protocol without compress

Appendix 3) Data collected

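### Does the severity comparison go wrong because 5.2.1 does not say how children without an ulcer are scored?

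*Combined protocol and SAP*

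**What the plan says.** The secondary objective in 2.2.1 reads: "Compare the severity of pressure ulcers at the catheter/tube junction". Section 2.2.2 adds only that the NPUAP scale is the instrument. In 5.2.1 the analysis is a description by stage, "At each stage of the NPUAP scale, the number and percentage of patients will be presented", followed by "A Mann-Whitney test will be applied to compare the two groups".

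Section 4.5 describes the scale as "graded from 1 to 4, with stage 1 being the least severe", so it has no zero. At catheter removal the assessor notes "presence or absence of pressure ulcers and NPUAP grade, if applicable". Under 4.6 that assessment, "reported on a data collection sheet will be considered as the source data". The appendix that lists the data items appears in the document by title only ("Appendix 3) Data collected"), so the coding of the grade for an ulcer-free child cannot be seen.

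The primary endpoint in 2.1.2 is "the occurrence of pressure ulcers of grade ≥ 1 on the NPUAP scale". Section 5.2.7 defines two analysis sets, intention-to-treat (all randomised patients) and per protocol, and attaches the first to the primary analysis. The missing-data rule in 5.2.5 counts a missing assessment as no ulcer, but for the primary endpoint only.

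**The concern.** Two analyses fit these sentences. One ranks every randomised child, with no ulcer below stage I. The other ranks only children who have a grade. The second could arise without anyone choosing it: if the grade field is blank where it does not apply, a rank test run on that field would drop those children.

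The second analysis has a known weakness. Its population is defined by a grade of 1 or more, which is the primary outcome, so randomisation no longer protects the comparison. If the compress prevents mainly stage I lesions, prevented ulcers leave the compress arm and those that remain are on average more severe. The test can then suggest that the compress makes ulcers worse although no child is worse off. The pilot is meant to inform a decision on a larger multicentre study (1.1), so a misleading secondary p-value would be unwelcome.

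**Working it through.** **Inputs.** From the plan: 360 randomised (5.2.2), 1:1 allocation (5.2.8), hence 180 per arm; a 15-point difference, 80% power, 5% alpha (5.2.2). The plan gives no ulcer rate or stage mix, only that lesions seen in the department are mainly stage I (1.1). All rates below are assumptions.

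**The plan's own figure.** Two-proportion formula, two-sided, pooled variance under the null, 55% against 40%:

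n per arm = [1.960·√(2·0.475·0.525) + 0.8416·√(0.55·0.45 + 0.40·0.60)]² / 0.15² = (1.384 + 0.588)² / 0.0225 = 172.8, rounded up to 173, so 346 in total.

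This matches 5.2.2. It has no direct bearing on the severity test, but 55% against 40% is a reasonable anchor for the first scenarios.

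**One data set, two readings.** Assume none / stage I / stage II counts of 90 / 72 / 18 in the control arm and 135 / 27 / 18 in the compress arm. The statistic is P(control worse) plus half the ties.

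- All children, no ulcer = 0: [72·135 + 18·(135 + 27) + ½(90·135 + 72·27 + 18·18)] / 180² = (12,636 + 7,209) / 32,400 = 0.61, p = 0.00002, favouring the compress.
- Ulcerated only, 90 against 45: [18·27 + ½(72·27 + 18·18)] / (90·45) = (486 + 1,134) / 4,050 = 0.40, p = 0.014, favouring control.

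So the direction can reverse on the same data.

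**How often.** Simulation with 180 per arm, 200,000 trials per scenario, tie-corrected Mann-Whitney at two-sided 5%:

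| Assumed rates, control to compress | Ulcerated-only: harm | All children 0 to 4: benefit |
|---|---|---|
| Stage I 45% to 30%, stage II 10% in both arms | 19.0% | 69.9% |
| same, stage II 5% | 12.9% | 76.8% |
| same, stage II 2% | 8.3% | 81.1% |
| same, stage II 1% | 5.6% | 82.5% |
| same, no stage II | 0% | 83.6% |
| Proportional fall, 45% + 10% to 32.7% + 7.3% | 2.6% | – |
| Stage II falls more, 45% + 10% to 36% + 4% | 0% | – |

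With 30% control incidence and 15 points of stage I prevented, harm signals reach 11.6%, 18.0% and 39.8% for stage II at 1%, 2% and 5%. In an extreme case (stage I 45% to 20%, stage II 10% in both arms) they reach 55.6%. The chance rate in one direction is 2.5%.

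**Would it be seen?** In the first scenario the expected stage I / stage II counts are 81/18 (0.45·180 and 0.10·180) against 54/18 (0.30·180 and 0.10·180). The share of ulcers at stage II rises from 18/99 = 18% to 18/72 = 25%, while the number of stage II ulcers is the same. The table planned in 5.2.1 shows exactly this. Where stage I alone falls and a false harm signal occurs, the primary chi-square is significant for benefit in the same trial in 82% to 99.8% of cases.

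**What a fixed 0-to-4 rule would buy.** Across the scenarios, that test gives the same verdict as the primary chi-square in 84% to 99% of trials (99.8% with no stage II). If incidence is equal and stage II doubles (45% + 10% against 35% + 20%), it detects the shift in 16% of trials, against 82% for the ulcerated-only test and 77% for a comparison of stage II or worse over all randomised children.

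**The case for a change.** The case for a change is that the omission is real and cheap to close. No section states the set, the score or the denominator; 5.2.5 and 5.2.7 are worded for the primary analysis; and the objective, the scale without a zero and the conditional recording of a grade all support the ulcerated-only reading. The reversal above shows that the choice can matter, and two or three sentences written before analysis would prevent a choice made after seeing the data.

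The omission stands, and so does the point that an ulcerated-only test conditions on the primary outcome. The step to a defect in the plan does not.

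- The stage line in 5.2.1 counts patients, and the two groups there are the randomised arms throughout. Section 5.2.7 offers no ulcerated-only set. Presence or absence is noted for each child, and a threshold of grade 1 or more puts no ulcer below stage I. Together these lean towards all randomised children without settling it.
- That a blank grade would drop children is an inference about coding that the published document does not show.
- The harm signal needs three things together: the ulcerated-only reading, some stage II ulcers, and a compress that prevents stage I while largely sparing stage II. Nothing in the plan supports the third; its rationale is less pressure on the skin, which does not single out stage I.

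**Conclusion.** No change to the plan follows. This is an unwritten rule for one secondary test in a single-centre pilot, of the kind an analyst settles sensibly before looking at the data, with the text already leaning towards all randomised children. The possible distortion runs from none (proportional fall, or no stage II ulcers) to 19.0% false harm signals with stage I falling from 45% to 30% and stage II at 10%, and higher under less favourable assumed mixes. It would be legible from the planned stage counts, and the primary chi-square is unaffected.

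Nor is there one right replacement. Scoring 0 to 4 keeps the randomised comparison but largely repeats the primary result; ranking ulcerated children answers the severity question more directly but is conditional on having an ulcer. The choice between them is a trade-off. These conclusions rest on assumed incidences and stage mixes, since 5.2.2 states that no such data exist. That the omission exists is certain; the size of any effect is not known.

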5.2.2. Statistical justification of the number of subjects

This is a pilot study. To our knowledge, there are currently no data on the assessment of pressure ulcers at the junction of the catheter with the extension tube or peripheral venous line tubing in paediatric hospitalised patients.

This study will therefore provide reliable data on these pressure ulcers in both standard care (without compresses) and will also provide data on the benefits of compresses for pressure ulcer prevention.

With a total of 346 patients, our study will highlight a difference of at least 15% between the two groups (80% power and 5% alpha risk). **In order to guarantee the power of the study, a total of 360 patients will be randomised.**

5.2.3. Expected degree of statistical significance

The alpha risk is set at 5%.

5.2.4. Statistical criteria for stopping the research

NA

5.2.5. Method for handling missing, unused or invalid data

All missing data and the reasons for their absence will be described in each group.

For the analysis of the primary endpoint, in the event of missing data, we will consider the absence of pressure ulcers (regardless of the randomisation group).

5.2.6. Management of changes to the initial strategy analysis plan

NA

5.2.7. Selection of individuals to be included in the analyses

The primary analysis will be performed on the intention-to-treat (ITT) population, i.e. all randomised patients.

A complementary analysis will be performed on the Per Protocol (PP) population, including randomised patients for whom no major deviations from the protocol have been identified.

A data review meeting will be organised to review and define whether each deviation is a major criterion or not.

5.2.8. Randomisation

Randomisation will not be stratified.

It will be carried out according to a 1:1 ratio and will be performed in blocks.

Randomisation will be performed using Ennov Clinical by connecting to the website: <https://nantes-lrsy.hugo-online.fr/EnnovClinical/login>. Connection will be made using a login, password and study code provided by the data manager of the Clinical Research Unit at La Roche sur Yon Hospital. The following information must be provided:

- First initial of surname,
- First initial of the first name,
- Month and year of birth,
- Compliance with inclusion and exclusion criteria (yes/no),

Randomisation will be carried out after confirmation of the patient's eligibility for inclusion in the study. The inclusion number will be assigned automatically during randomisation.

The randomisation list will be drawn up by the statistician at the Research Unit of La Roche sur Yon Hospital. An explanatory guide to randomisation will be available online at Ennov Clinical.

6. SAFETY EVALUATION

In the context of this Interventional Research with Minimal Risks and Constraints (RIPH Category 2), adverse events (whether serious or not) do not need to be reported to the sponsor. Notification must be made as part of the vigilance system established for the product or practice being researched (pharmacovigilance for a drug, material vigilance for a medical device, etc.) in accordance with the regulations in force.

Only "new developments" and malfunctions that may interfere with the research must be reported to the sponsor without delay after they become known so that corrective measures can be put in place. For these malfunctions, the investigator may use the reporting form provided by the institution's internal vigilance system, which is anonymised (patient inclusion number only).

A new development is any new information that could lead to a reassessment of the benefits and risks of the research or the product being researched, to changes in the use of this product, in the conduct of the research, or in the documents relating to the research, or to the suspension, interruption or modification of the research protocol or similar research.

The sponsor shall immediately inform the competent authority and the human subjects review committee of the new facts and, where applicable, the measures taken, from the day on which they become known.

7. ADMINISTRATIVE AND REGULATORY ASPECTS

7.1. RIGHT OF ACCESS TO SOURCE DATA AND DOCUMENTS

Each patient's medical data will only be disclosed to the sponsor or any person duly authorised by the sponsor and, where applicable, to the competent health authorities, under conditions that guarantee confidentiality.

The sponsor and the supervisory authorities may request direct access to the medical file to verify the procedures and/or data of the clinical trial, within the limits authorised by laws and regulations.

7.2. DATA CONFIDENTIALITY

Persons with direct access shall take all necessary precautions to ensure the confidentiality of information relating to the persons involved, in particular with regard to their identity and the results obtained.

These persons, like the investigators themselves, are subject to professional secrecy (under the conditions defined by Articles 226-13 and 226-14 of the Penal Code).

During or at the end of the research, the data collected on the individuals involved and transmitted by the participants shall be anonymised.

Under no circumstances shall the names or addresses of the persons concerned be disclosed.

Only the first two letters of the subject's surname and the first letter of their first name will be recorded, accompanied by a coded number specific to the study indicating the order of inclusion of the subjects.

7.3. COMPUTERISED DATA AND SUBMISSION TO THE CNIL

This study falls within the scope of the "Reference Methodology" (MR-001) in accordance with the provisions of Article 54, paragraph 5, of Law No. 78-17 of 6 January 1978, revised in June 2018, relating to information technology, files and freedoms. The CHD Vendée de La Roche sur Yon, promoter of the study, has signed a commitment to comply with this "Reference Methodology".

7.4. *MONITORING OF THE TRIAL*

Monitoring will be carried out by the Promotion Department of the Research Directorate. A Clinical Research Associate (CRA) will visit each site (investigator) regularly to carry out quality control of the data reported in the observation notebooks.

The protocol has been classified according to the estimated level of risk for patients participating in the research. It will be monitored as follows:

Risk A: low or negligible foreseeable risk

On-site monitoring visits will be organised after appointment with the investigator. CRAs must be able to consult the following at each site:

- the data collection notebooks for the patients included,
- the patients' medical and nursing records,
- the investigator's file.

7.5. *INSPECTION/AUDIT*

An inspection or audit may be conducted as part of this study. The sponsor and/or participating centres must be able to provide inspectors or auditors with access to the data.

7.6. *ETHICAL CONSIDERATIONS*

7.6.1. *Informed consent*

The investigator (nurse) undertakes to obtain the patient's free, informed and express consent after providing them with information about the protocol.

Minors who are not emancipated will receive information adapted to their level of understanding, both from the investigator and from their parents or guardians (who will themselves be informed by the investigator).

They will be consulted to the extent that their condition allows. Their personal consent to participate in the research will be sought. Their refusal or revocation of consent cannot be overridden.

As the patients are minors and this is research involving human subjects with minimal risks and constraints in accordance with the decree published on 3 May 2017 establishing the list of such research, express informed consent is required from both parents.

However, in the context of this study, children admitted to paediatric emergency departments are rarely accompanied by both parents. Given that randomisation must be carried out before a peripheral venous line is inserted, which is necessary for the administration of a prescribed treatment that may need to be administered without delay, it will therefore be difficult to obtain the written consent of both parents before it is put in place. Under these circumstances, only the written consent of the parent present will be obtained after verbal consent has been given by the absent parent.

The investigator will provide a copy of the information sheet and a consent form to the person(s) with parental authority. The patient may only be included in the study after having read the information sheet, which will be explained to them in accordance with their level of understanding, and given their verbal consent if they are old enough to understand, and the person(s) with parental authority have given their written consent, after having been given time to consider the matter, if necessary.

The investigator must also sign and date the consent form. Two copies of these two documents will be provided on paper so that the patient (or those with parental authority) and the investigator can each keep a copy. The investigator's original copy will be filed in the investigator's binder. If consent is signed in duplicate, the investigator will keep the original and the duplicate will be given to the patient.

The patient's information and verbal agreement to participate in the research must be noted in their medical file. Written consent will be given by the person(s) with parental authority.

For minors who reach the age of majority during their participation, confirmation of their consent will be required after appropriate information has been provided.

Other requests for exemption from the obligation to obtain the signed consent of both parents may be submitted to the CPP in the following cases:

- if one of the parents is deceased
- if the child is recognised by only one parent

- if only one parent has been designated as the holder of parental authority by court order
- in cases of separated or divorced parents

In these cases, only the signed consent of the parent accompanying the child and holding parental authority will be obtained.

In the case of separated parents, if the second parent (holder of parental authority) who did not sign the initial consent form wishes to withdraw their child from the study, their decision will of course be taken into account.

7.6.2. Committee for the Protection of Persons

The sponsor undertakes to submit the study proposal to a Committee for the Protection of Persons (CPP) for prior authorisation. The information provided relates, on the one hand, to the methods and nature of the research and, on the other hand, to the safeguards provided for patients participating in the trial.

7.7. *INFORMATION TO THE COMPETENT AUTHORITIES*

This protocol will be submitted to the ANSM for information.

7.8. *AMENDMENTS TO THE PROTOCOL*

Requests for substantial amendments shall be submitted by the sponsor to the relevant CPP for its opinion, to the ANSM for information, and to the relevant Committee for the Protection of Persons for authorisation/information, in accordance with the law in force and its implementing decrees.

The amended protocol must be updated and dated.

The patient information and consent forms must be amended if necessary.

